2.4.7.2 Pharmacodynamic variables

2.4.7.2.1 Mutational profiling in circulating free DNA

Descriptive statistics of the type of genomic aberrations at baseline will be provided. The prevalence of patients with mutations for each gene and the overall genomic profile of patients (annotated with the treatment arm and possibly other patients' characteristics) will be described. For some key genes of interest, additional analyses may be performed by treatment arm to better understand the circulating mutational profile of patients. To this end, the description of each aberration or the distribution of the mutant allele frequency, mutant concentration and abnormal

copy number variant will be also described through descriptive statistics. Some associations with baseline or pharmacodynamic variables (eg, the baseline or % change from baseline of Ki67, the change in ER expression H-Score) will be presented through descriptive statistics and graphical presentation.

The genomic aberrations detected in the cfDNA will be compared to the ones identified from the tumor biopsies.

2.4.7.2.2 Tumor biopsy analyses

The additional protein biomarkers (PgR, BCL-2, Cyclin D1 and potentially other proteins) will be analyzed similarly to the ER protein (see [Section 2.4.5.2](#)).

For tumor-related RNA data, the measurements at baseline and after a 14-day treatment in addition to the change from baseline will be described per treatment arm for each gene signature (eg, ER activation score) or immune scores by descriptive statistics and graphical visualization.

For tumor-related DNA data, the prevalence of patients with mutations for each gene and the overall genomic profile of patients (annotated with the treatment arm and possibly other patients' characteristics) will be described at baseline. For some key genes of interest, additional analyses may be performed by treatment arm to better understand the tumor mutational profile of patients. To this end, the description of each aberration at baseline or the evolution of the mutant allele frequency/copy number variation over time will be also described through descriptive statistics and graphical visualization. Some associations with baseline or pharmacodynamic variables (eg, the baseline or % change from baseline of Ki67, the change in ER expression H-Score) will be presented through descriptive statistics and graphical presentation. The tumor mutational burden score and the microsatellite instability will be also described with descriptive statistics per treatment arm.

2.4.8 Further therapy after discontinuation of investigational medicinal product administration during the study

A summary table will be provided for further anti-cancer therapies based on WHO-DD coding. Similar analysis will be performed for further radiotherapy.

A listing of surgery information, including the date and type of surgery, and the reason of surgery not performed (if any) will be provided.

2.4.9 Pharmacokinetic/Pharmacodynamic analysis

2.4.9.1 PK / PD analyses

Graphical presentation of SAR439859 PK concentrations (and possibly PK parameters of interest) will be done in regards of efficacy/PD endpoints. Efficacy/PD endpoint would include but may not be limited to Ki67 expressed as % change from baseline, change in ER expression H-Score or ER activation score (degradation). Plasma concentrations below LLOQ will be replaced by LLOQ/2.

2.4.9.2 Concentration-ECG analyses

Exploratory plots

The relationship between change from baseline of ECG parameters and SAR439859 concentrations will be first explored graphically, in order to investigate any potential delayed or sustained effects and the type of modeling to be done, using the following plots, by treatment group:

- Plot of mean (\pm SEM) change from baseline in ECG data and mean SAR439859 concentration versus time (hours post-dose) overlaid onto the same plot.
- A scatterplot for PK plasma concentration versus change from baseline in ECG parameter, including trend lines (simple linear regression and loess line)

Concentration - ECG analyses will be performed for the QTcF, heart rate, PR and QRS intervals.

Time-matched pharmacokinetic concentrations will be used.

Modeling

In case of direct and linear relationship between concentrations and change from baseline in ECG parameters (QTcF, HR, PR, and QRS), a linear mixed effect model will be carried out, with population intercept, fixed terms for nominal time, with the concentration (slope) and the baseline ECG parameter (centered baseline values: subject's baseline minus the mean of the overall population) as covariates, and with random terms for individual subject deviation from the population intercept and slope, using SAS Proc Mixed. The analysis model was the following:

Change from Baseline in ECG parameter_{ij} = ($\alpha + A_i$) + $\gamma \times$ Baseline ECG_i + C \times Time_j + $\beta \times$ Concentration_{ij} + e_{ij}

with:

- α and β are the fixed population intercept and concentration slope.
- γ is the fixed effect for the baseline ECG slope
- A_i is the random intercept for the i^{th} subject, with A_i assumed to be normally distributed with null mean and an unstructured variance-covariance matrix per subject block.
- C is the fixed effect associated with Time_j (0 for pre-dose of D14 and 1 for 3h post-dose of D14)
- e_{ij} represents i.i.d. standard normal errors.

The estimates of each effect of the model, along with their 95% confidence interval, will be provided. In addition, prediction of change from baseline in ECG parameters at selected concentrations (geometric mean concentration at 3h of D14 for each dose) will be also calculated from the model (estimates and 90% confidence intervals). The scatter plot of individual ECG values versus PK concentrations with the regression line overlaid will be also provided.

Goodness-of-fit and residual plots will be provided. In case of lack of fit (ie, the linear model is not adequate), alternative models will be explored, like linear models using transformed concentration values (eg, logarithmic concentrations) or nonlinear models (E_{\max} or sigmoid E_{\max} models).

The following goodness-of-fit plots were provided:

- Model observed versus predicted change from baseline in ECG (delta ECG)
- Quantile-Quantile plots of residuals
- Distribution of residuals
- Residual plots for concentration, centered baseline ECG and time
- Quantiles of concentration and change from baseline ECG overlaid with slope of the final model

Effect of SAR439859 on heart rate will be evaluated by plotting the time course of the mean change from baseline in heart rate by dose.

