Viral serologies	X						Viral serologies include hepatitis A antigen or IgM hepatitis A antibody, HBs antigen or hepatitis B viral DNA, hepatitis C antibody or quantitative hepatitis C viral (HCV) ribonucleic acid (RNA).
Single 12-lead ECG	X						See Section 8.2.3 for details.
Triplicate ECG		X		X			Electronic records of triplicate ECG are required at pre-dose on D1 and at pre-dose and 3h post-dose on D14. See Section 8.2.3 for details.
Vital signs	X	(X)	X	X			These assessments will be repeated within 1 day prior to the first dosing of IMP if abnormal or if screening assessment >7 days of D1. See Section 8.2.2 for details.
Patient diary distribution		X					
Patient diary review			X	X			
Amcenestant administration 400 mg QD		Continuous once a day (QD)					Study treatment should be taken in the morning. Study treatment duration is planned for 14 days, and should not exceed 14 days. IMP will be dispensed at the study site visits on D1. On D1 and D14, IMP will be taken on-site after fasting tests and pre-dose assessment. See Section 6.1 for details.
Amcenestant administration 200 mg QD		Continuous once a day (QD)					
Letrozole administration		Continuous once a day (QD)					

Procedure ^a	Screening	Treatment Period (14 days)			Surgery ^c	Post treatment safety follow-up period	Notes
	up to 14 days before randomization	D1 ^b	D7 (±2)	D14	D15 (+1)	30 (±7) days after last IMP intake	
Tumor Biopsy ^d	X				X		Participant selection is based on the biopsy at diagnosis analyzed in a local lab. A new core-cut biopsy (baseline sample) should be performed prior to the first dosing of IMP, as well as a core-cut biopsy from surgery specimen or new core-cut biopsy after the last IMP intake for study purpose. Alternatively, tissue from the diagnostic biopsy may be used for the baseline sample if certain criteria are fulfilled. Baseline and post-treatment biopsy will be centrally examined. See Section 8.6.1 for details.
Tumor size by ultrasound	X			X			Measurement of tumor size using ultrasound at screening (baseline) and on D14. At screening, tumor size assessed by ultrasound will also be used for inclusion criteria. See Section 8.1.2 for details.

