8.5 PHARMACOKINETICS

- Pharmacokinetic sampling is planned only in participants randomized in amcenestant treatment arms.
- Blood samples of approximately 1 mL will be collected for measurement of plasma concentrations of amcenestant as specified in the SoA ([Section 1.3](#)) using a validated liquid chromatography-mass spectrometry/mass spectrometry assay. Instructions for the collection and handling of PK samples will be provided by the Sponsor in the laboratory manual.
- Samples will be used to evaluate the PK of amcenestant. Samples collected for analyses of amcenestant plasma concentration may also be used to evaluate safety or efficacy aspects related to concerns arising during or after the study.
- It is of utmost importance to collect all blood samples at the specified time windows and according to the specifications (refer to the laboratory manual).
- Samples missed or lost for any reason should be recorded. Actual dates and times (24-hour clock time) of blood collection should be recorded. Actual dates and times of previous drug administration should also be precisely recorded.

For the comfort of the participants, some PK samplings may be deleted during the course of the study if they are no longer deemed necessary by the Sanofi PK team.

Any changes in the timing or addition of time points for any planned study assessments must be documented and approved by the relevant study team member and then archived in the Sponsor and site study files but will not constitute a protocol amendment. The IRB/IEC will be informed of any safety issues that require alteration of the safety monitoring scheme or amendment of the ICF.

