2.3.6 Pharmacokinetic/pharmacodynamic population

PK/PD population is defined as all treated subjects as long as they had at least one pharmacodynamic assessment time-matched with pharmacokinetic parameters of interest. The specific population will be defined for each PK/PD analysis.

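### The concentration-ECG model is in effect fitted without letrozole, so its predicted 3 h change is not a drug effect; its text and equation also disagree on the random slope

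*SAP*

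**What the plan says.** SAP 2.4.9.2 (Modeling) applies if the exploratory plots suggest a direct linear relation. For QTcF, heart rate, PR and QRS it models

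change from baseline = (α + A_i) + γ × baseline + C × time + β × concentration + error.

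- **Fixed terms.** "α and β are the fixed population intercept and concentration slope". The time term reads: "C is the fixed effect associated with Time_j (0 for pre-dose of D14 and 1 for 3h post-dose of D14". There is no treatment or control term.
- **Random terms.** The prose asks for a model "with random terms for individual subject deviation from the population intercept and slope, using SAS Proc Mixed". The equation and its list of symbols contain only a random intercept A_i, with an unstructured covariance.
- **Outputs.** Each model effect with a 95% interval, and the predicted change from baseline at the Day 14 3 h geometric mean concentration of each dose, with a 90% interval.

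On the population, SAP 2.3.6 says: "PK/PD population is defined as all treated subjects as long as they had at least one pharmacodynamic assessment time-matched with pharmacokinetic parameters of interest". It adds: "The specific population will be defined for each PK/PD analysis". Section 2.4.9.2 gives no such definition.

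On the data, Protocol 8.5 says: "Pharmacokinetic sampling is planned only in participants randomized in amcenestant treatment arms". The Schedule of Activities (Protocol 1.3) says: "Electronic records of triplicate ECG are required at pre-dose on D1 and at pre-dose and 3h post-dose on D14". That ECG entry is not limited to any arm. SAP 2.4.6.5 summarises ECG changes by treatment group, which includes letrozole.

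**The concern.** The trial is randomised and plans triplicate ECGs in all three arms at the same times, yet the model that predicts the ECG change at each amcenestrant dose appears to use only the amcenestrant arms. Day 1 has a pre-dose ECG only, so the Day 14 3 h record has no baseline at the same time of day. Anything unrelated to the drug that moves the ECG between Day 1 and Day 14, or between pre-dose and 3 h, therefore enters the predicted change, and no control is subtracted. Such a shift could look like a drug effect or hide one.

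The disagreement on random effects is a separate fault. The prose and the equation describe two different models with different standard errors for the slope, and a programmer cannot tell which to fit.

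**Working it through.** **1. Figure to reproduce.** The documents give no numerical figure for this analysis. The check is therefore algebra, then simulation and generalised least squares (GLS) under stated assumptions.

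**2. Who enters the model.** Every record needs a concentration. PK is sampled only in the amcenestrant arms (Protocol 8.5), and the PK/PD population needs a PK-matched assessment (SAP 2.3.6). Letrozole drops out by inference.

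**3. What each term absorbs.** At mean baseline, where the centred baseline term is zero:

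- Day 14 pre-dose: α + β × pre-dose concentration
- Day 14 3 h: α + C + β × 3 h concentration

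Drift from Day 1 goes into α and the pre-dose to 3 h change goes into C. β is identified by concentration differences between patients and doses. The reported 3 h prediction is the whole sum α + C + β × concentration.

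**4. Simulation of the SAP model, amcenestrant arms only.** Random-intercept GLS with known variances, 2,000 runs per row.

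- From the documents: 42 per arm as planned (SAP 1.3); clearance 14.5 L/h, the middle of the stated 14–15, and CV 45% (Protocol 4.3).
- Assumed: 3 h to pre-dose concentration ratio 2, between-patient SD 8 ms, residual SD 6 ms.
- Average concentration at 400 mg is 400 / (14.5 × 24) = 1.15 mg/L. The 3 h value is 1.15 × √2 = 1.63 mg/L. A slope of 3 ms per mg/L then gives about 4.89 ms.

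| Drift (ms) | Time of day (ms) | True drug effect (ms) | Reported prediction (ms) | β × concentration (ms) |
|---|---|---|---|---|
| 0 | 0 | 0 | 0.08 | −0.03 |
| +2 | 0 | 0 | 2.01 | −0.06 |
| 0 | +3 | 0 | 2.98 | −0.06 |
| +2 | +3 | 0 | 5.03 | −0.04 |
| +5 | +5 | 0 | 10.05 | 0.00 |
| −5 | −5 | 0 | −9.95 | −0.03 |
| +2 | +3 | 4.89 | 9.85 | 4.83 |
| −5 | −5 | 4.89 | −5.12 | 4.88 |

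The prediction equals drift + time of day + drug effect, up to simulation error; in the last row −5 − 5 + 4.89 = −5.11. The slope recovers the drug effect throughout.

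Adding letrozole at concentration 0 does not by itself correct the prediction: in the +2/+3 row with no drug effect it is 5.02 ms. A contrast between arms is needed. Letrozole does sharpen the slope, whose SE falls from 1.13 to 0.86 ms per mg/L, that is 1 − 0.86/1.13 = 24%. This run has no separate arm intercept.

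**5. Precision with an arm intercept.** Assumed: between-patient SD 7 ms, residual SD 6 ms, CV 45%, trough to 3 h ratio 0.2–0.6, 400:200 exposure ratio 1.5–2, and 25–40 patients per arm. The SAP says enrolment stopped early but gives no number.

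- The slope SE falls by about 8–27%. The gain is largest at ratio 0.2 and exposure ratio 1.5, and smallest at 0.6 and 2.
- At 35 per arm and the 400 mg concentration, the SEs are:
  - uncontrolled prediction: 1.1–1.2 ms
  - β × concentration without letrozole: about 2.2–2.4 ms
  - difference from letrozole: 1.8–1.9 ms
- At the 200 mg concentration, β × concentration has SE of roughly 2.2/2 = 1.1 to 2.4/1.5 = 1.6 ms. The letrozole contrast is about 1.7 ms, because it keeps the arm intercept. Its precision advantage over β × concentration therefore holds at 400 mg only.

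**6. Random effects.** A random intercept and slope with unstructured covariance has three variance parameters plus the residual: four in all. Two records per patient supply two variances and one covariance. Only the spread of concentrations between patients helps to identify the fourth. With A_i alone, an unstructured covariance has nothing to structure.

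**The case against.** The strongest reply is that the drug effect in this model is β, and β is sound. A reader might infer that drift and time-of-day change are counted as amcenestrant effect throughout the analysis. The documents do not support that: α and C are there to take those shifts, and the table shows β unaffected when the linear model holds. The time term is a protection, not the fault. Correlation between time and concentration costs precision but does not cause bias, and the SAP plans residual plots and alternative models if the fit is poor. α, C and β are each reported, so β × concentration can be worked out.

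A reader might also infer that the SAP deliberately excludes letrozole. No sentence does so; the population is simply undefined. Protocol 9.4.3 also allows a dedicated PK/PD SAP, which is not among these documents.

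It can further be said that the prediction is correctly labelled as a change from baseline, that letrozole changes appear descriptively in SAP 2.4.6.5, and that the analysis is exploratory and conditional, with no decision attached.

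Most of this stands, and it limits the point. The labelling defence is weaker: the end of SAP 2.4.9.2 proposes to evaluate the effect of amcenestrant on heart rate from mean change from baseline by dose, which treats an uncontrolled change as a drug effect. β × concentration without letrozole also relies on extrapolating to zero concentration with no patient there. Nothing in the reply removes the conflict over the random slope.

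**Conclusion.** The point holds in limited form. As written, the model in effect uses the amcenestrant arms only. Its slope is not biased by drift or time of day under the stated linear model. Its predicted 3 h change carries both one for one, in either direction, and should not be read as a drug effect. Leaving out zero-concentration records also makes time and concentration harder to separate, at a cost in slope SE that letrozole data would cut by about 8–27%.

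The drift and time-of-day values are illustrations. The SDs, concentration ratios and achieved sample size are assumptions, because the documents give none of them. The random-slope conflict is a plain contradiction and needs no assumption. Since the analysis is exploratory, this is a minor-to-moderate point.

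**What to change.** In SAP 2.4.9.2:

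- Define the analysis population, and include the letrozole Day 14 pre-dose and 3 h ECGs with amcenestrant concentration set to 0.
- Add an amcenestrant-versus-letrozole intercept.
- Keep the planned prediction and report next to it, for each dose, the predicted difference from letrozole at the 3 h geometric mean concentration. α and C cancel in that difference, provided the time effect is common to the arms.
- Make prose, equation and covariance statement agree: a random intercept, with a random slope only if two records per patient support it.

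The cost is SAP wording and one refit on ECGs already in the schedule. The contrast has a wider interval than the uncontrolled prediction, and it is relative to letrozole, an active drug, not to placebo.

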2.5 DATA HANDLING CONVENTIONS

2.5.1 General conventions

Not applicable. Renal function parameter including eGFR will be collected directly via CRF.

2.5.2 Data handling conventions for secondary efficacy variables

Not applicable.

2.5.3 Missing data

The analyses and summaries of continuous and categorical variables will be based on observed data only. Percentages will be calculated using as denominator the number of patients with non-missing observation in the considered population. When relevant, the number of patients with missing data is presented.

Handling of disease characteristics missing/partial dates

- If the day is missing, it will be imputed by 1.
- If the month is missing, it will be imputed by 1 (only for medical history variables).
- If the year is missing, no imputation will be performed.

Incomplete date of cancer diagnosis:

- If the day of the cancer diagnosis is missing, the date will be imputed to the first day of the month.
- If day and month of the cancer diagnosis are missing, no imputation will be done.

Handling of medication missing/partial dates

No imputation of medication (other than anti-cancer therapies) start/end dates or times will be performed. If a medication date or time is missing or partially missing and it cannot be determined whether it was taken prior or concomitantly, it will be considered a prior and concomitant medication.

Imputation of incomplete date for post anti-cancer treatment start date

For post anti-cancer treatments, if the medication start date is missing, it will be imputed as follows:

- If the medication start day and month are missing and the medication start year is the same as treatment end year, the medication start date will be set equal to treatment end date +1.
- If the medication start day and month are missing and the medication start year is after the treatment end year, the medication start day and month will each be set to 01.
- If the medication start day is missing and medication start year and month is the same as the treatment end year and month, the medication start date will be set to the treatment end date +1.
- If the medication start day is missing and medication start month is before the treatment end month and the medication start year is the same as treatment end year, the medication start day will be set to 01.
- If the medication start day is missing and the medication start month is after the treatment end month and the medication start year is the same as treatment end year, the medication start day will be set to 01.
- If the medication start day is missing and the medication start month is not missing and the medication start year is after the treatment end year, the medication start day will be set to 01.
- If the medication start day, start month and start year is missing, the medication start date will be set equal to the treatment end date +1.

Handling of computation of treatment duration if investigational medicinal product end of treatment date is missing

- For the calculation of the treatment duration, the date of the last dose of IMP is equal to the date of last administration reported on the end-of-treatment case report form page. If this date is missing, the exposure duration should be left as missing.

Handling of adverse events when date and time of first investigational medicinal product administration is missing

- When the date and time of the first IMP administration is missing, all adverse events that occurred on or after the day of randomization should be considered as treatment-emergent adverse events. The exposure duration should be kept as missing.

Missing grade

If the grade is missing for one of the treatment emergent occurrences of an AE, the maximal severity on the remaining occurrences will be considered. If the severity is missing for all the occurrences, no imputation will be done and missing grades will be summarized in the “all grades” category.

Handling of missing assessment of relationship of adverse events to investigational medicinal product

If the assessment of the relationship to the regimen is missing, then the relationship to the regimen has to be assumed and the adverse event considered as such in the frequency tables of possibly related adverse events, but no imputation should be done at the data level.

Handling of potentially clinically significant abnormalities

If a patient has a missing baseline he will be grouped in the category “normal/missing at baseline.”

For PCSAs with 2 conditions, one based on a change from baseline value or a normal range and the other on a threshold value, with the first condition being missing, the PCSA will be based only on the second condition.

For a PCSA defined on a threshold and/or a normal range, this PCSA will be derived using this threshold if the normal range is missing; eg, for eosinophils the PCSA is >0.5 GIGA/L or $> \text{ULN}$ if $\text{ULN} \geq 0.5$ GIGA/L. When ULN is missing, the value 0.5 should be used.

Measurements flagged as invalid by the laboratory will not be summarized or taken into account in the computation of PCSA values.

